Preterm birth complicates 13% of all pregnancies worldwide and is the most important cause of neonatal morbidity and mortality.² Although disability-free survival rates have increased over the years as a result of improved facilities and treatments, preterm birth is still accountable for 75% of all perinatal deaths and >50% of morbidities.^{3,4}

Women with a history of a preterm delivery have a distinctly increased risk to deliver preterm in a subsequent pregnancy. This risk ranges from 17,2% with one previous preterm delivery up to 28% for two previous preterm deliveries.⁵ This also applies to women with a history of a second trimester fetal-loss after 20 weeks of gestation who show an increased risk of 12% for preterm birth in a subsequent pregnancy.⁶ Yet another independent risk factor for PTB is a previous cervical surgery; after a single surgical conisation the risk of PTB increases almost 5 fold and after two even 10-fold.⁷

Confidential

Evidence based treatment guidelines for these high-risk pregnancies are not available in Germany, expectant management is the usual care for these patients. The European Association of Perinatal Medicine⁸ and the Society for Maternal-Fetal Medicine Publications Committee (SMFM)⁹ recommends for the US 17-alpha hydroxyprogesterone caproate (17-OHPC) therapy for women with a history of PTB in a subsequent singleton pregnancy. But this is not a treatment option for the majority of European countries as the drug is only available in some EC-countries on basis of old regime accreditations. The SMFM-statement details that vaginal progesterone should not be considered a substitute for 17-OHPC, whereas the European guideline does not differentiate between 17-OHPC and vaginal progesterone.

Up to now the risk factor previous PTB has only been investigated in RCTs for 17-OHCP^{10, 11, 12, 13} or in RCTs where the risk factor previous PTB was combined with the risk factor cervical shortening (vaginal progesterone^{14, 15}; cerclage¹⁶, 17-OHP¹). Looking at the evidence of therapeutic effectiveness of vaginal progesterone these risk factors should be addressed separately. Vaginal progesterone proved to be ineffective in the prevention of recurrent PTB^{14, 15} but effectively reduced PTB in women with a short cervix^{17, 18}.

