Every center will receive a password and a username in order to access the database for recruitment, randomization and documentation of patient data. Hereby, a personal identification number will be assigned for every patient. Patient names will not appear in the databases.

This database will be supervised and coordinated by PD [name], Bürgerhospital Frankfurt/M. (Webmaster).

4.8. Identification of data to be collected in the case report files (CRF) that should be considered as data source.

Data will be collected in E-CRF, provided by >[name] Wissenschaft, Berlin< on study software "Castor".

4.9. Definition of what is considered to be the end of the study.

The study will be finished after the 3 year-follow up examination of the surviving children focusing on neurodevelopmental disabilities.

5. Selection and withdrawal of subjects

5.1. Inclusion criteria.

- Women with a singleton pregnancy and a history of at least one previous preterm delivery before 34+0 weeks and/or a history of previous cervical surgery
- 12+0 -16+0 weeks of gestation
- Minimal age of 18 years
- Informed consent signature

5.2. Exclusion criteria.

- Major fetal abnormalities (requiring surgery or leading to infant death or severe handicap)
- Cerclage prior to randomisation
- Uterine malformation
- Placenta previa totalis
- Active vaginal bleeding at the moment of randomization
- Spontaneous rupture of membranes at the time of randomization
- Silicone allergy
- Painful regular uterine contractions
- Current participation in another RCT

5.3. Withdrawal criteria.

If a participant may voluntarily withdraw from treatment or if it is necessary to remove the pessary due to the conditions described before, the patients will be followed as usual until delivery (intention-to-treat analysis).

Replacement of patients is not applicable in this trial.

5.4. Rescue treatment criteria.

Regarding the control group, a McDonald cerclage may be indicated if there is a cervical shortening below 25 mm during the follow-up scans according to the current guidelines and expert recommendations¹¹.

6. Treatment of Subjects

6.1. Treatments to be administered.

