It will be left to the investigator's clinical judgment whether or not an AE is of sufficient severity to require the participant's removal from treatment. A participant may also voluntarily withdraw from treatment due to what he or she perceives as an intolerable AE. If either of these occurs, the participant must undergo an end of study assessment and be given appropriate care under medical supervision until symptoms cease or the condition becomes stable.

A medically qualified investigator will assess the relationship of AEs to the study medication.

All SAEs must be reported to the main investigator. He will perform an initial check of the report, request any additional information, and he will notify it to the Ethics Committee. All SAE information will be recorded. It may be appropriate that some SAEs do not require immediate reporting but this must be justified. Justification might be determined, for example, by admission to hospital, or prolongation of hospitalization, where this is to be expected in the underlying disease or condition.

All adverse events (AE) life-threatening or resulting in death will be notified within 24 hours. All AE that are not life-threatening will be notified within 15 days. The rest of AE will be recorded and analyzed at the end of the study.

9. Statistics

9.1. Description of statistical methods.

A descriptive analysis by preterm birth will be carried out calculating means and medians for quantitative variables and proportions for categorical variables.

The primary statistical aim is to compare the primary combined outcome "long-term survival without neuro-developmental disability at 3 years follow up" between the two treatment groups with a two-sided chi-square test. In general, statistical comparisons will be two-sided and use appropriate tests according to the scale of the outcome. A multivariate logistic regression will be fitted to control for possible confounders. Relative risks and 95% confidence interval as well as adjusted odds ratios will be calculated for the binary outcomes. Statistical significance will be accepted in all cases with a $p \leq 0.05$.

The main statistical evaluation will be performed at two time points.

(1) The complete data set for the secondary endpoints will be available after the last women enrolled in this study has delivered her neonate, so the analysis of these outcome parameter will be done right after this event.

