(2) The primary outcome will be evaluated 3 years after the last woman enrolled in this study has delivered her neonate.

Confidential

A descriptive analysis by preterm birth will be carried out calculating means and medians for quantitative variables and proportions with 95% confidence intervals for categorical variables.

Additionally we will perform an explorative subgroup analysis of the study collective comparing the efficacy of the cervical pessary treatment in women with a normal cervical length at 12 -16 weeks of gestation and in women who have developed a cervical shortening (< 25 mm) as an additional risk factor.

For the primary endpoint we expect to have a drop out rate of up to 25% due to the long follow-up time (3 years) of the study; but we do not expect to have lost data for the secondary endpoints because for these parameters the study has a short follow-up time till time to birth only.

An interim analysis shall be conducted on key safety parameters after birth of 150 neonates: the following safety endpoints will be assessed by a one-sided test with $\alpha=1\%$

- on level of the neonates:

rate of preterm birth, time to birth, birth weight, death, neonatal morbidity, harm of intervention

- and on the maternal level:

rate of hospitalisation for threatened preterm labour < 32 weeks, rate of P_{RoM} <32 weeks, rate of infection / inflammation, rate of physical or psychological intolerance to pessary, rate of SAR/SAE, death.

The trial will be terminated as negative if a disadvantage for the pessary-treatment can be found in one of these tests. To guarantee a high safety level the significance level is chosen more conservatively than in a Bonferroni correction. All analysis will be carried out with SPSS® version 19.0 or later (IBM Company SPSS Inc.

Headquarters, Chicago, Illinois, USA) and R version 3.2.3 or later (R Foundation for Statistical Computing, Vienna, Austria).

Primary Outcome	Statistical Test
Children`s Long-Term Survival without Neurodevelopmental Disability (3-Years-follow up)	Chi-Square test
Secondary Outcome	Statistical Test
Birth before 34 Weeks of Gestation	Chi-Square test or Fisher test
Time to Birth	Cox regression
Birthweight	t-test or Wilcoxon-Mann-Whitney test
Fetal / Neonatal Death	Chi-Square test or Fisher test
Neonatal Morbidity	Chi-Square test or Fisher test
Need for Hospitalization	Chi-Square test or Fisher test
Days of Hospitalization	t-test or Wilcoxon-Mann-Whitney test

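### Qualifying history (previous preterm birth, cervical surgery, or both) is a baseline factor that no planned analysis names; stratifying the primary test by it and reporting by route would be a modest, nearly free improvement.

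*Combined protocol and SAP*

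**What the plan says.** Section 5.1 admits women with a singleton pregnancy and "a history of at least one previous preterm delivery before 34+0 weeks and/or a history of previous cervical surgery". Three groups therefore qualify: preterm birth only, surgery only, and both. Under section 13 the website allocates a woman only once she meets the inclusion criteria, and sections 4.7 and 13 give each centre its own list. No stratification by qualifying history is stated.

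Section 9.1 compares the primary outcome "between the two treatment groups with a two-sided chi-square test", and its table of tests repeats the chi-square. It then adds: "A multivariate logistic regression will be fitted to control for possible confounders". Relative risks "as well as adjusted odds ratios will be calculated for the binary outcomes". The covariates are not named, so qualifying history is neither promised nor excluded.

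The one efficacy subgroup is exploratory and contrasts the effect "in women with a normal cervical length at 12 -16 weeks of gestation and in women who have developed a cervical shortening".

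The background (section 2.1) treats the two histories as separate risk factors for preterm birth. For previous preterm birth: "This risk ranges from 17,2% with one previous preterm delivery up to 28% for two previous preterm deliveries". For surgery: "after a single surgical conisation the risk of PTB increases almost 5 fold and after two even 10-fold".

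**The concern.** Qualifying history is settled before allocation, so it can be used in the analysis without any risk of being affected by treatment. If it predicts the primary outcome, a test that ignores it gives up some power, and the main estimate takes no account of a chance imbalance in routes between the arms.

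The second issue is interpretation. The trial gives one pooled answer for two populations for which section 2.1 describes separate and thin evidence on the pessary. If the effect differed by route, a pooled null or a pooled benefit would be applied to both, and no planned table would let a reader look. The cervical-length subgroup does not fill this gap. It is a different factor, and one of its two groups is defined by shortening that may develop after randomisation.

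**Working it through.** **Inputs from the documents.** Rates of 20% (control) and 8% (pessary), two-sided alpha 5%, 80% power, 121 evaluable and 155 recruited per arm (synopsis, section 9.2). Dropout is 25% in the synopsis and section 9.1 but 15% in section 9.2. I read 20% and 8% as rates of the adverse outcome (death or disability), because with the pessary at 8% they do not make sense as disability-free survival.

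**Assumed, because not given.** Share of women in a route: 30%, 50% or 70%. Ratio of control-arm risk between routes: 1 to 5.

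**1. The plan's own figure.** n = [1.96·√(2·0.14·0.86) + 0.8416·√(0.20·0.80 + 0.08·0.92)]² / 0.12² = (0.9618 + 0.4068)² / 0.0144 = 130.1, so 131 per arm. The stated 121 is not reproduced. It gives 77.1% power by this formula and 78.4% by exact enumeration of the Pearson test. After 25% dropout, 155 × 0.75 ≈ 116 remain, with 75.3% and 76.4%. This is a separate matter and does not drive the comparison below.

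**2. Plain against stratified test.** Simulation at 121 per arm, two routes, overall 20% versus 8%, common odds ratio. Plain chi-square power is about 78.4% throughout. Mantel-Haenszel power:

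| Control risk ratio between routes | Higher-risk route 30% of women | 50% | 70% |
|---|---|---|---|
| 1 (not prognostic) | 78.1% | 78.0% | 78.1% |
| 1.5 | 78.3% | 78.3% | 78.3% |
| 2 | 78.8% | 78.8% | 78.6% |
| 3 | 80.6% | 79.9% | 79.2% |
| 5 | 83.2% | 81.3% | 79.7% |

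The change is about -0.4 to +2.2 points up to a ratio of 3, and +4.8 at most. At 116 per arm with a common risk ratio of 0.4, the change is about -0.2 (not prognostic), +0.3 (ratio 1.63), +1.6 (3) and +3.7 (5). Type I error of the stratified test stays at about 5%, and three strata work without a merging rule.

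**3. Effect confined to one route.** Take 20% control risk in both routes, 8% on pessary in one and 20% in the other. With share f, the pooled pessary rate is 0.20 - 0.12f. For f = 0.5 it is 14%, so the difference halves to 6 points. At 121 per arm, power = Φ{[0.06 - 1.96·√(2·0.17·0.83/121)] / √[(0.16 + 0.1204)/121]} = Φ[(0.06 - 0.0947)/0.0481] = Φ(-0.72) = 24%.

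Interaction on the risk difference, f = 0.5, 60.5 per arm per route: SE = √(0.2336/60.5 + 0.32/60.5) = 0.0957, and power = Φ(0.12/0.0957 - 1.96) = Φ(-0.71) = 24%.

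| Share of route with effect | Overall test | Test within that route | Interaction |
|---|---|---|---|
| 30% | 11% | 31% | 22% |
| 50% | 24% | 48% | 24% |
| 70% | 43% | 62% | 20% |

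At 116 per arm the overall figures are 11%, 23% and 42%.

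**4. Precision by route.** With 58 per arm in each of two routes (116/2), the 95% half-width is 1.96·√(0.2336/58) = 12.4 points at 20% versus 8%, and 1.96·√(0.32/58) = 14.6 points at 20% in both arms. That is as wide as the planned 12-point effect.

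**The case against.** The strongest reply is that nothing here is broken. The chi-square is a valid test in a randomised trial, its p-value and interval already allow for chance imbalance, and it matches the sample-size calculation. Pooling the two histories is the declared objective. An adjusted analysis is planned. All of that stands, and it is why this is an improvement and not a correction.

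A reader might infer from section 2.1 that the routes carry clearly different risks, so that precision is certainly lost. The documents do not support this. The 17.2% and 28% are one against two preterm births, a contrast inside one route; their ratio of 1.63 serves above only as an illustrative value. The 5-fold rise after conisation has no stated reference rate. All these figures concern preterm birth, not death or disability at 3 years. If route is not prognostic, stratifying costs a fraction of a point.

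A reader might also infer that a route analysis would rescue an effect present in only one route. It would not. The Mantel-Haenszel test also gives one pooled answer, and the interaction test has about 20-24% power. Nor do the documents suggest that the effect differs by route; the scenario shows the limits of the design, not an expectation.

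Two practical objections have weight. Merging sparse strata after seeing the data would put a data-dependent choice inside the primary analysis, so the strata must be fixed. And the CRF fields are not listed: confirming an and/or criterion does not prove that the route itself was recorded.

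**Conclusion.** The point holds as an efficiency and interpretation improvement. Neither the primary test nor any planned subgroup uses qualifying history, and the secondary model leaves its covariates open, so they could be chosen after the data are seen.

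The gain in power is small and conditional: about -0.4 to +2 points for control risk ratios between routes of 1 to 3, and up to about 4 to 5 points at a ratio of 5, which nothing in the documents establishes. These figures assume 20% versus 8% overall, 116 to 121 evaluable per arm, a common treatment effect across routes, and route shares of 30% to 70%.

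The firmer part is transparency: pre-specified estimates by route would let a reader see whether the two populations look alike, though this trial cannot settle that question.

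**What to change.** In section 9.1, before outcome data are seen:

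- Make the primary comparison a Mantel-Haenszel test with pooled risk difference and risk ratio over three fixed strata: previous preterm birth before 34+0 only, cervical surgery only, both. Allow no merging that depends on the data.
- Keep the plain chi-square as a sensitivity analysis.
- Name qualifying history as a covariate in the planned logistic regression.
- Report the treatment estimate with 95% CI by route, labelled exploratory. State that the interaction test has only about 20-24% power and so can neither confirm nor exclude an effect confined to one route.
- Confirm that the eCRF holds qualifying history in these three categories.

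The centre randomisation lists can stay as they are. The cost is SAP wording and a few lines of code, with no extra patients or visits. If the eCRF lacks the field, it must be completed from the eligibility records. The downside is a loss of a fraction of a power point if route is not prognostic, and imprecise route-specific estimates.
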